6.10. Safety Analyses

Safety analyses will be performed on the safety population and classified by the actual treatment group unless specified. Safety descriptive statistic summaries may also include all LY3298176 doses combined if appropriate. Unless specified otherwise, safety listings will display values/events during all study periods; key adverse events (AEs) summaries will be presented separately for the treatment period and for the treatment period and follow-up period combined if applicable. Any events/values reported after start of rescue therapy but before the start of the follow-up period will be included in safety analyses for the treatment period.

Safety measures will include extent of exposure, vital signs, physical characteristics, treatment-emergent adverse events (TEAEs; including serious adverse events [SAEs]), adverse events of special interest (AESIs; that is, injection site reactions, hypersensitivity reactions, hypoglycemia episodes, GI events - nausea, vomiting, and diarrhea-, acute pancreatitis, and major adverse cardiovascular [CV] events), laboratory measures (including hematology, chemistry, urinalysis, and samples collected for testing for anti-LY3298176 and antibodies), and electrocardiograms (ECGs). In addition, the change from baseline to 26 weeks in HDL-C, total cholesterol, triglycerides, and LDL-C will be analyzed on the mITT population.

The summary statistics for continuous variables will be sample size, mean, SD, median, minimum, and maximum. If applicable (for example, in the case of MMRM analyses) these descriptive statistics may also include LS means, LS means standard error (SE), and 95% CI for each treatment group as well as for LY3298176 difference from placebo.

The summary statistics for categorical variables will be sample size, frequency, and percentage.

Additional analyses, such as concentration-safety lab plots, may be performed if warranted upon review of the data.

6.10.1. Vital Signs

Vital sign measurements (that is, systolic blood pressure [SBP] and diastolic blood pressure [DBP; mmHg] and pulse rate [PR; beats/minute]) will be collected according to the Study Schedule of Events (Appendix 1). The average 3 measurements for BP and PR is going to be calculated and analyzed; however, values obtained from fewer than 3 measurements will also be included in summaries and analyses.

Descriptive statistics will be provided by treatment arm for change from baseline at each visit for SBP, DBP, PR. Figures will display LS mean values for change from baseline at each visit for the LY3298176 groups versus placebo and dulaglutide.

The change from baseline for the above measures will be analyzed using an MMRM-based model as described in Section 6.1.1. on two analysis sets: mITT and mITT population on treatment without rescue.

The frequency and percentage of patients showing vital sign results in each of the categories specified in Table 6.4 will also be summarized by treatment and visit.

Table 6.4. Vital Sign Summary Categories

Vital Sign Measure	Unit	Low	High
Systolic Blood Pressure	mmHg	≤90 and decrease ≥20	\geq 160 and increase \geq 20
Diastolic Blood Pressure	mmHg	≤50 and decrease ≥10	\geq 100 and increase \geq 10
Pulse Rate	bpm	<50 and decrease ≥15	>100 and increase ≥15

A Bayesian analysis for pulse rate will be performed to assess the probability of the posterior distribution of the change in HR from baseline of 26 weeks for each LY3298176 treatment dose arm compared to placebo

$$Pr(\Delta LY - \Delta Placebo \le 10 \text{ bpm}|Data)$$

The mixed effect linear model will be used to fit the response for treatment i, subject j and time k:

$$Y_{ijk} = \mu_{ik} + s_{ij} + e_{ijk},$$

where μ_{ik} is the mean response for treatment i at time point k, and $s_{ij} \sim N(0, \sigma_s^2)$ and $e_{ij} \sim n(0, \sigma^2)$ are independent. The analysis will be performed on mITT population on treatment without rescue medication.

All vital signs and physical characteristics measurements will be listed, for all randomized patients.

6.10.2. HDL-C, Total Cholesterol, Triglycerides, and LDL-C

Change from baseline in HDL-C, total cholesterol, triglycerides, and LDL-C will be analyzed using the MMRM model described in Section 6.1.1.

6.10.3. Adverse Events

No statistical tests will be performed to compare AE rates between treatment groups.

Treatment-emergent AEs, defined as events that are newly reported after randomization or reported to worsen in severity from baseline, will be determined based on occurrence on or after the date of first dose of investigational product. Since the eCRF does not collect dosing time, it is acknowledged that there is a possibility that a small number of TEAEs could actually have onset prior to the time of first dose.

Adverse events will be summarized as TEAEs. Summaries of TEAEs will be presented for the combined treatment and follow-up periods, and the treatment period only.

Adverse event summary tables will include a "Total LY3298176" column for all LY3298176 treatment groups combined if appropriate.

In summaries by System Organ Class (SOC) or Preferred Term (PT), SOC will be displayed in alphabetical order and PT will be displayed by decreasing frequency of the "Total LY3298176" patient incidence within each SOC. In summaries by PT, PT will be displayed by decreasing frequency of the "Total LY3298176" patient incidence. Ordering by frequency should be based on percentages and not on frequency counts.

All AEs (not only TEAEs) will be presented in listings by patient, actual term, PT, severity and relationship to treatment (yes, no). Listings will also include treatment group, start date and stop date (or ongoing), assessment of seriousness, relationship to nonstudy drug treatment (study disease, study procedure, none), relationship to study device (yes, no), action taken with study medication and outcome of AE.

Listings will report data as recorded (for example unknown severity or relationship and partial or unknown dates). Where necessary, such as for determination of TEAEs, partial or unknown dates will be imputed.

6.10.3.1. All Treatment-Emergent Adverse Events

The incidence of patients with at least 1 TEAE and the incidence of TEAEs will be summarized, showing frequency and percentage of patients, by SOC, PT, and treatment group. The total number of TEAEs and the number of TEAEs for each SOC and PT will also be reported for each

treatment group. Chi-square test will be performed for overall comparison between treatments if deemed appropriate.

The patient incidence of TEAEs will also be summarized by SOC, PT, maximum severity, and treatment group.

6.10.3.2. Related Adverse Events

The incidence of patients with at least 1 TEAE assessed as related (including possibly related or unknown) and the patient incidence of related TEAEs will be summarized by SOC, PT, and treatment group. In addition, the total number of related TEAEs and the number of related TEAEs for each SOC and PT will be reported for each treatment group.

6.10.3.3. Serious Adverse Events

A listing of all SAEs by patient will be produced. If a sufficient number of SAEs are reported (that is, >1 SAE overall per treatment group or >3 SAEs in any 1 treatment group) summary tables will be produced showing the incidence of patients with at least 1 SAE and the patient incidence of SAEs by SOC, PT, and treatment group. In addition, if a sufficient number of SAEs are reported, the total number of SAEs and the number of SAEs for each SOC and PT will be reported for each treatment group.

6.10.3.4. Adverse Events Leading to Discontinuation

Treatment-emergent AEs reported with an action taken of "drug withdrawn" will be summarized, using patient incidence, by SOC, PT, and treatment group. In addition, a listing of AEs leading to discontinuation of study treatment (that is, with action taken as "drug withdrawn") will be presented.

Treatment-emergent AEs reported as reason for study discontinuation (that is, discontinuation of study procedures as well as study treatment) will be summarized, using patient incidence, by SOC, PT, and treatment group. In addition, a listing of AEs leading to discontinuation of study will be presented.

6.10.3.5. Most Common Adverse Events

The most common TEAEs, determined as TEAEs occurring in \geq 5% in any LY3298176 arm, will be summarized by SOC, PT, and treatment group. This summary will also include the number of such events by SOC, PT, and treatment group.

6.10.3.6. Deaths

All deaths recorded on the status page, the AE page, or the SAE page (with a death date, cause of death, outcome or SAE categorization present) of the CRFs will be considered a death for summary purposes. All deaths (CV or non-CV) that occur during the treatment period or follow-up period will be adjudicated by an independent central adjudication committee in compliance with a study-specific adjudication charter. Results of the adjudication will be entered in the death adjudication eCRF page.

A listing of adjudicated results will include the adjudicator assessment of death type, whether or not the adjudicator's assessment of the event date agrees with the investigator's assessment of

the event date, and the date of the event, showing the adjudicator's assessment in the case of non-agreement. If adjudicated results show >1 death per treatment group or >3 deaths within any 1 treatment group, a summary table will present patient incidence of deaths by SOC, PT, and treatment group.

6.10.4. Adverse Events of Special Interest

Adverse events of special interest to be identified and described during this study are injection site reactions, hypersensitivity reactions, hypoglycemia, acute pancreatitis, major adverse CV events, and selected GI events (nausea, vomiting, and diarrhea).

Descriptive statistics for AESIs will be presented by treatment group and visit. Continuous responses will be summarized using sample size, mean, SD, median, minimum and maximum, while categorical responses will be summarized using sample size, frequency and percentage.

If data warrant, continuous elements of AESIs (such as the duration of hypoglycemaic events) will be analyzed using an MMRM-based model described in Section 6.1.1.

In addition, for AESIs with information collected on the AE eCRF page (that is, hypersensitivity reactions, acute pancreatitis, and major adverse CV events) summary tables will be presented only if >3% of patients has the AESI. The incidence of patients with at least 1 AESI and the patient incidence of AESIs will be summarized, showing frequency and percentage of patients, by SOC (if applicable), PT, and treatment group. The total number of AESIs and the number of AESIs for each SOC (if applicable) and PT will also be reported for each treatment group.

Listings by patient will be provided for AESIs. Listings will also present adjudication information by patient for adjudicated events.

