10.3.4.7. Adverse Events of Special Interest

Hypoglycemia, hypersensitivity reactions, injection site reactions, acute pancreatitis, major adverse CV events, and selected GI events such as nausea, vomiting, and diarrhea are defined as AESIs.

Descriptive statistics for the AESIs will be presented by treatment group and visit. Continuous responses will be summarized using sample size, mean, SD, median, minimum, and maximum, whereas categorical responses will be summarized using frequencies and percentages.

Continuous elements of AESIs, such as the durations of hypoglycemia and injection site reactions, will be analyzed using a similar MMRM-based model as for the secondary analysis on the primary endpoint.

Statistical analyses on categorical AESIs will be analyzed using a logistic regression analysis with fixed effects of treatment, metformin use, and HbA1c strata. Additional analyses will be run if necessary.

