6.1. General Considerations

Statistical analysis of this study will be the responsibility of Lilly or its designee. Any change to the statistical methods described in the protocol will require an amendment only if it changes a principal feature of the protocol. Any other change to the statistical analyses and the justification for the change will be documented in the clinical study report. Additional exploratory analyses of data may be conducted as deemed appropriate without further changes made to the protocol or SAP even after the database lock (DBL).

Tests of treatment effects will be conducted at a one-sided alpha level of 0.1 and/or one-sided 90% credible interval (CI) for the Bayesian dose response analysis, and at a two-sided alpha level of 0.05 for other analyses, unless otherwise stated. No adjustments for multiplicity will be performed.

The baseline visit will be Visit 3. The baseline values used for the analyses will be the last scheduled baseline value obtained for each patient prior to first dosing. For all variables, if baseline data are not available or if they are missing, then the last non-missing measurement taken prior to first treatment will be used for the baseline measurement.

All efficacy and safety data will be summarized by each treatment group at each scheduled visit unless otherwise indicated. A scheduled visit is based on the actual visit number reported by the site. Imputed data may be applied in model-based data analysis, but will not be used in data listing.

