6.1.1. Analysis of Repeated Measures

The mixed model for repeated measures (MMRM) using restricted maximum likelihood (REML) will be used to fit change from baseline values at all scheduled visits. The model will include the treatment group, strata (that is, baseline HbA1c category, baseline BMI category, and metformin use [yes, no]), visit, and treatment-by-visit interaction as fixed effects, baseline value of the dependent variable as a covariate, and patient as a random effect. If the analysis is on the primary endpoint, baseline HbA1c category will not be included in the model in addition to the continuous covariate of baseline HbA1c. To model the covariance structure within patients, the unstructured covariance matrix will be selected initially. If the unstructured covariance structure leads to nonconvergence, the following covariance structures will be tested in order:

- toeplitz with heterogeneity
- autoregressive with heterogeneity
- compound symmetry with heterogeneous variances
- toeplitz
- autoregressive
- compound symmetry without heterogeneous variances
- compound symmetry

The first covariance structure that converges will be used.

Kenward-Roger method will be used to estimate the denominator degrees of freedom and the restricted maximum likelihood approach will be used to determine the model estimates.

The MMRM model will present least squares (LS) mean estimates for each scheduled week by treatment group and 2-sided 95% CIs for mean changes from baseline within and (when warranted) between treatments. T-statistics corresponding to the Type III sums of squares for the differences in the LS means will be used to obtain p-values for treatment group comparisons.

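### Durations of special-interest events are assigned to a change-from-baseline MMRM that cannot be fitted to them as written

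*SAP*

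**What the plan says.** SAP 6.10.4 states, on the condition that the data warrant it, that "continuous elements of AESIs (such as the duration of hypoglycemaic events) will be analyzed using an MMRM-based model", pointing to SAP 6.1.1. Protocol 10.3.4.7 has no such condition and also names injection site reactions: "Continuous elements of AESIs, such as the durations of hypoglycemia and injection site reactions, will be analyzed using a similar MMRM-based model".

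SAP 6.1.1 defines the model. It "will be used to fit change from baseline values at all scheduled visits", with "baseline value of the dependent variable as a covariate, and patient as a random effect". T-statistics for differences in least squares means "will be used to obtain p-values for treatment group comparisons". Under SAP 6.1, testing is "at a two-sided alpha level of 0.05 for other analyses, unless otherwise stated. No adjustments for multiplicity will be performed".

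Baseline in SAP 6.1 is the last scheduled value before first dosing. For nausea, vomiting and diarrhea, SAP 6.10.4.3 computes duration for each event as stop date minus start date.

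Occurrence is handled elsewhere. SAP 6.10.4.4 gives per-patient monthly rates, incidence by visit and overall, and a logistic regression for total hypoglycemia. SAP 6.10.4.3 summarises incidence and maximum severity of the gastrointestinal events. Protocol 10.3.4.7 plans logistic regression for categorical AESIs.

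**The concern.** The cited model needs a baseline measurement and a value at each scheduled visit. An event duration supplies neither. The plan does not say what value an event-free patient has, or how several events between two visits become one observation. An analyst would have to invent an adaptation.

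The obvious adaptation drops the change score and fits durations where they exist. Event-free patients then count as missing. SAP 6.9.2.3 notes that MMRM is consistent under missing at random, but these values are not missing, because no event occurred. Having an event is a post-randomisation outcome that treatment can change, so the arms would no longer be comparable by design. A dose that causes many extra short events could show a shorter mean duration, with a p-value attached, in a study where tolerability across doses is an objective.

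**Working it through.** **Step 1. Can the model be fitted?**

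- *Baseline.* Injection site reactions cannot precede the first injection. Diary review from Visit 2 might catch a few lead-in hypoglycemic events, but no baseline duration is scheduled. Outcome and covariate are therefore both undefined. If baseline were set to 0 for everyone, the covariate would be constant and its coefficient could not be estimated.
- *Covariance.* There are 9 post-baseline visits that are not PK-specific (Visits 4, 6, 8, 10, 11, 13, 14, 15 and 16). An unstructured matrix has 9 × 10 / 2 = 45 parameters. With 50 patients per arm and an assumed control incidence of 5%, 10% or 20%, about 2.5, 5 or 10 control patients would have any event.
- *Coding zeros instead.* Giving event-free patients 0 at each visit keeps everyone in, but produces an outcome that is mostly zeros and unsuited to a normal-errors MMRM.
- *Protocol cross-reference.* Protocol 10.3.4.7 cites the secondary analysis of the primary endpoint. That section (10.3.3.3.1) describes a dose–response noninferiority model. The MMRM is in 10.3.3.2, where the outcome is again change from baseline.

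**Step 2. What could an analysis of event patients only show?**

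The documents attach no figure to this analysis, so there is none to reproduce. Arm size checks: 45 / (1 − 0.10) = 50, and 6 × 50 = 300, as in SAP 5.3.

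The documents give no event rates or durations. All of the following are assumptions:

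- control incidence p_c and dose incidence p_d of 5%/15%, 10%/30% or 20%/50%
- mean duration of 60 min on control
- mean of 66 min on the dose for patients who would have had an event anyway
- added events lasting m = 20, 40 or 60 min on average
- lognormal durations with log-SD 0.5.

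Formulas:

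- dose burden per randomised patient = p_c × 66 + (p_d − p_c) × m
- dose mean among event patients = that burden / p_d
- control burden per randomised patient = p_c × 60.

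For 10%/30% and m = 20, the dose burden is 0.10 × 66 + 0.20 × 20 = 10.6 min, against 0.10 × 60 = 6.0 on control. The dose mean among event patients is 10.6 / 0.30 = 35.3 min, against 60.

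The last two columns come from 4,000 simulated trials per row at 50 per arm. A two-sample t-test among event patients stands in for one visit of the MMRM. Trials with fewer than two event patients in either arm are left out.

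| p_c / p_d | m (min) | Mean among event patients, dose v control | Minutes per randomised patient, dose v control | Dose looks better | Nominally significantly better |
|---|---|---|---|---|---|
| 5% / 15% | 20 | 35.3 v 60 | 5.3 v 3.0 | 89.1% | 26.1% |
| 5% / 15% | 40 | 48.7 v 60 | 7.3 v 3.0 | 69.5% | 10.2% |
| 5% / 15% | 60 | 62.0 v 60 | 9.3 v 3.0 | 42.2% | 2.9% |
| 10% / 30% | 20 | 35.3 v 60 | 10.6 v 6.0 | 94.3% | 33.7% |
| 10% / 30% | 40 | 48.7 v 60 | 14.6 v 6.0 | 74.7% | 13.9% |
| 10% / 30% | 60 | 62.0 v 60 | 18.6 v 6.0 | 42.2% | 2.5% |
| 20% / 50% | 20 | 38.4 v 60 | 19.2 v 12.0 | 97.0% | 44.0% |
| 20% / 50% | 40 | 50.4 v 60 | 25.2 v 12.0 | 78.2% | 15.0% |
| 20% / 50% | 60 | 62.4 v 60 | 31.2 v 12.0 | 41.8% | 2.0% |

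At 45 per arm the pattern is the same. Over both arm sizes, the dose looks better in 70–97% of trials when added events are shorter (20 or 40 min), and in 40–45% when they last 60 min. In every row the dose is worse per randomised patient.

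**The case against.** Much can be said against giving this weight.

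- *The SAP analysis is conditional.* This stands. Only the protocol is unconditional, and protocol 10.3.1 lets the SAP describe changes that do not touch a principal feature.
- *Neither document restricts the analysis to patients with events.* This stands. A reader might infer that the plan commits to a biased contrast. What the text shows is a model that does not fit the variable and no rule for adapting it. The restriction is one likely adaptation.
- *Event burden is already covered.* This largely stands. For hypoglycemia, rates, incidence and the logistic regression would show an excess of events. For nausea, vomiting and diarrhea, the incidence summaries would show it, although SAP 6.10.4 does not repeat the protocol's logistic regression for categorical AESIs.
- *No decision rule uses duration.* This stands. The MMRMs named for the second interim are for HbA1c and body weight. Safety data inform dose selection in general, but nothing ties this result to it.
- *The reversal depends on the inputs.* This stands. It needs added events to be shorter than usual ones.
- *Duration may not be available.* Protocol 9.2.1.2.4 lists it for nausea, vomiting and diarrhea. The items listed for injection site reactions (protocol 9.2.1.2.1, SAP 6.10.4.2) and hypoglycemia (protocol 9.2.1.2.3) do not include it, although these are the two event types that the protocol names for the MMRM. This limits the remedy and does not rescue the model.

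None of these points supplies a baseline for a duration or a value for an event-free patient.

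**Conclusion.** The point holds as a minor correction to a safety analysis. The MMRM of SAP 6.1.1 cannot be fitted to event durations as written, and an adaptation limited to patients with events would not be a randomised comparison. That contrast could favour a dose that adds many short events. The size shown rests wholly on assumed incidences and durations, with no systematic reversal when added events are as long as usual ones.

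A reader might infer that a worse dose would come out as better tolerated overall. The documents do not support that, because incidence and rates are reported separately and would show the excess. Only the duration result and its unadjusted p-value are at risk.

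**What to change.** Delete the MMRM and its p-values for AESI durations from SAP 6.10.4, and note that this replaces the sentence in protocol 10.3.4.7. Report duration per event descriptively among patients with events, showing the number of such patients in each arm.

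If a between-arm comparison is wanted, limit it to event types for which duration is captured. On the protocol's lists these are nausea, vomiting and diarrhea.

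- *Variable:* days with the event per patient over the treatment period, in the safety population, with zero for event-free patients.
- *Counting:* stop date minus start date plus 1. The current definition scores a same-day event as 0, which would merge it with no event.
- *Test:* a stratified Wilcoxon test, or a negative binomial model on the day counts with an exposure offset. The negative binomial model suits whole days and should not be applied to continuous time.

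The cost is SAP wording and one derived variable for each such event type. No new data are needed for the gastrointestinal events. Hypoglycemia and injection site reactions should stay out of any such comparison unless their case report forms are confirmed to record duration.
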